8 CONCOMITANT MEDICATIONS

8.1 Prior, Concomitant and Prohibited Therapy

Current medications and any medications taken within the 30 days prior to the start of the study will be recorded as prior/concomitant medications (using their generic name, if known) with the corresponding indication, start and stop dates. The medications to be recorded include prescription, all over-the-counter (OTC) medications and all dietary supplements. All medications taken on a regular basis should be recorded prior to commencing the use of the investigational product. Any medications started during the study (including “as needed” medications) will be recorded in the concomitant medication list as soon as the Investigational Site will become aware of the medication being added.

Prohibited Therapies are those medicinal products and treatment methods that are not allowed during the study period and within the timeframes specified in Table 2.

Table 2. List of Prohibited Medication and Treatment Methods

Prohibited Topical Treatments:

Topical Treatment	Prohibited Time Frame prior to Baseline
Astringents or abrasives	2 days
RHOFADE™ (oxymetazoline HCl) Cream, 1%	1 week
Bleach baths	1 week
Mirvaso (brimonidine) topical cream	1 week
Vinegar	1 week
Topical Prescription/OTC medications for treatment of acne	2 weeks
Soolantra (Ivermectin 1%) topical cream	1 week
Topical Antibiotic	2 weeks
Use of over the counter antimicrobial	2 weeks
Benzoyl Peroxide	2 weeks
Immunomodulators	4 weeks
Oracea (doxycycline) topical cream	2 weeks
Corticosteroids	4 weeks
Electrocoagulation, Dermabrasion; Facial peels	4 weeks
Dermatologic/surgical procedure on the face	4 weeks
Topical Prescription medications for the treatment of rosacea (e.g. azelaic acid, metronidazole, etc.)	4 weeks

Laser, Phototherapy, Photodynamic Therapy or IPL (intense pulsed light) treatment	4 weeks
Over the counter topical retinoid use on the face	4 weeks

Prohibited Systemic Treatments:

Systemic Treatment	Prohibited Time Frame prior to Baseline
Exposed to excessive ultraviolet (UV) radiation and/or subject was unwilling to refrain from excessive exposure to UV radiation during the course of the study	1 week
Prescription anti inflammatory	2 weeks
Prescription/OTC anti-inflammatory medications (excludes low dose aspirin)	2 weeks
Systemic Antibiotics	4 weeks
Systemic medications for the treatment of rosacea (e.g. doxycycline, tetracycline, macrolides)	4 weeks
Prescription medications for treatment of acne	4 weeks
Corticosteroids (oral or injectable)	4 weeks
Immunomodulators	12 weeks
Oral retinoid use (e.g., isotretinoin), vitamin A supplements greater than 10,000 units/day	6 months

8.2 Prohibited procedures

Participants will be asked refrain from cosmetic facial procedures for the possible treatment of rosacea or acne, such as chemical peels, micro or dermabrasion, comedone extraction, electrocautery, Phototherapy, Photodynamic Therapy or IPL (intense pulsed light) treatment laser peels or laser light therapy (including ThermaClear™, blue light, tanning devices or photodynamic therapy), steroid injections throughout the study until the final follow-up visit.

If the Investigator becomes aware of a subject having taken a prohibited medication or performed prohibited procedure, they will report the incident to the Medical Monitor within 24 hours, and the Medical Monitor and/or Sponsor will provide written approval of the subject's continuation or discontinuation from the study.

9 LIFESTYLE RESTRICTIONS

9.1 Use of cleanser and moisturizer during the trial

At the beginning of the trial, subjects will be provided with cleanser and moisturizer to use for the duration of the trial as needed. The subject may choose not to use a moisturizer, as it is not required. If moisturizer is used, subject should be advised to apply it 10 minutes after the application of the IP.

Subjects may use other cleansers to wash other parts of their body not treated during the study.

At Week 8 (End of Investigational product application) subjects will be asked to return cleanser and moisturizer that was provided to them by the Sponsor and will be asked to go back to their regular regimen and use their preferred cleanser and moisturizer.

9.2 Use of makeup, moisturizers and sun screen

- Use of anti-aging, anti-acne or rosacea treatment products or procedures on the face will be prohibited during the study.
- Subjects will be encouraged not to use other topical products on the face, such as emollients, sunscreen, moisturizers, etc. These should be used minimally or used sparingly while in the active phase (Baseline-Week 8) of the trial.
- Participants will be advised to use minimally or use sparingly liquid or powder makeup during the active phase (Baseline-Week 8) of the study.

10 STUDY PROCEDURES AND SCHEDULE OF STUDY ACTIVITIES

The following sections describe the procedures to be completed during the study. Subjects are to be assessed by the same Investigator or site personnel whenever possible.

10.1 Administrative Procedures

10.1.1 Subject Informed Consent

A signed and dated, study-specific, approved by Institutional Review Board (IRB)/Independent Ethics Committee (IEC) and applicable regulatory authorities Informed Consent Form must be obtained from each subject prior to performing any study related procedures. No study related procedures or activities may be performed until each subject is fully informed and the consent form is signed and dated.

10.1.2 Documentation of Screen Failures

Investigators must account for all subjects who sign informed consent and will maintain an Subject Screening and Enrollment Log capturing subjects screened and indicating who was

enrolled or excluded and the reason why. If the subject is found not to be eligible prior to enrollment, the reason(s) for ineligibility must be documented by the Investigator. Subject Numbers assigned to subjects who fail screening will not be re-used.

10.2 Study Procedures

10.2.1 Visit 1- Screening Visit (Day -21 to -1)

- Informed Consent
- Inclusion/Exclusion Criteria
- Demographics
- Medical History
- Concomitant and Prohibited Therapies review and documentation
- Physical examination
- Collection of Vital Signs
- Urine pregnancy test for WOCBP
- Venipuncture for Laboratory Assessment & Urinalysis
- Investigator's Global Assessment [IGA]
- Clinician's Erythema Assessment [CEA]
- Skindex-16
- Patient Self-Assessment (PSA)
- Fitzpatrick skin type
- Start AE collection and assessment

10.2.2 Washout Phase (-14 to -1)

Washout phase may be initiated after Screening procedures have been completed.

10.2.3 Visit 2- Baseline visit (Day 1):

Baseline visit will include the following procedures and assessments:

- Review of inclusion/exclusion criteria
- Review of Medical History
- Concomitant and Prohibited Therapies review and documentation
- Physical examination
- Collection of Vital Signs
- Urine pregnancy test for WOCBP
- Venipuncture for Laboratory Assessment & Urinalysis
- Blood for biomarkers
- Investigator's Global Assessment [IGA]
- Clinician's Erythema Assessment [CEA]
- Skindex 16
- Patient Self-Assessment (PSA)

- Telangiectasia Evaluation
- Randomization
- IP dispensation
- IP compliance
- IP application under medical supervision
- Study cleanser and moisturizer dispensation
- Study counseling
- Study Diary
- Adverse Events collection and assessment

10.2.4 Visit 3- Week 1 (Day 7) ±2 days

The following procedures will be performed:

- Concomitant and Prohibited Therapies review
- Collection of Vital Signs
- Investigator's Global Assessment [IGA]
- Clinician's Erythema Assessment [CEA]
- Skindex 16
- Patient Self-Assessment (PSA)
- Study Counseling
- Study Diary
- Urine pregnancy test for WOCBP
- Adverse Event collection and assessment

10.2.5 Visit 4- Week 4 (Day 28) ±2 days

The following procedures will be performed:

- Concomitant and Prohibited Therapies review
- Collection of Vital Signs
- Venipuncture for Laboratory Assessment & Urinalysis
- Investigator's Global Assessment [IGA]
- Clinician's Erythema Assessment [CEA]
- Skindex 16
- Patient Self-Assessment (PSA)
- Urine pregnancy test for WOCBP
- Study cleanser and moisturizer dispensation
- IP compliance
- IP collection
- IP dispensation
- Study Counseling
- Study Diary

- Adverse event collection and assessment

10.2.6 Visit 5- Week 8 (Day 56) ±2 days

The following procedures will be performed:

- Concomitant and Prohibited Therapies review
- Collection of Vital Signs
- Venipuncture for Laboratory Assessment & Urinalysis
- Blood for biomarkers
- Investigator's Global Assessment [IGA]
- Clinician's Erythema Assessment [CEA]
- Skindex 16
- Patient Self-Assessment (PSA)
- Telangiectasia Evaluation
- Urine pregnancy test for WOCBP
- IP collection
- IP compliance
- Study cleanser and moisturizer collection
- Study Counseling
- Study Diary
- Adverse event collection and assessment

10.2.7 Visit 6- End of Study Visit-Week 12 (Day 84) ±2 days

The following procedures will be performed:

- Concomitant and Prohibited Therapies review
- Physical Exam
- Collection of Vital Signs
- Urine Pregnancy Test for WOCBP
- Investigator's Global Assessment [IGA]
- Clinician's Erythema Assessment [CEA]
- Skindex 16
- Patient Self-Assessment (PSA)
- Adverse event collection and assessment

10.2.8 Unscheduled Visit

If an event arises that requires subject to come in to the research center, subjects should be scheduled for the Unscheduled visit and assessments are performed based on investigator discretion.

Subjects will be encouraged to report any complications or adverse effects during their participation. Investigator may evaluate the subject at an unscheduled visit, if subject's condition will be considered as worsening.

10.2.9 Early Termination Visit

Every attempt should be made to complete all visits during the defined window periods. Subjects who do not complete all required study visits and withdraw from the study before Week 12 final visit, will be asked to complete the Early Termination Visit.

During the visit, the following will be obtained:

- Concomitant and Prohibited Therapies review
- Physical Exam
- Collection of Vital Signs
- Urine Pregnancy Test for WOCBP
- Venipuncture for Laboratory Assessment & Urinalysis
- Blood for biomarkers
- Investigator's Global Assessment [IGA]
- Clinician's Erythema Assessment [CEA]
- Skindex 16
- Patient Self-Assessment (PSA)
- Telangiectasia Evaluation
- IP collection
- IP compliance
- Study cleanser and moisturizer collection
- Study diary
- Adverse event collection and assessment

11 METHODS OF ASSESSMENT

11.1 Clinical Evaluations

Study activities will take place according to the Schedule of Study Activities table. The following clinical evaluations will be conducted during the course of the study.

11.1.1 Subject Demographics

Basic demographic information, including date of birth, Fitzpatrick skin type (classification of skin type (or phototype) depending on the amount of melanin pigment in the skin), gender, ethnicity, and race will be recorded at the Screening Visit.

11.1.2 Medical history

Medical history will be collected at the Screening Visit. Relevant medical history, including past history of rosacea will be documented.

11.1.3 Concomitant Medication Recording

All medications (both prescription and nonprescription, and including vitamins, herbals, topicals, inhaled, and intranasal) taken within 30 days prior to the start of the investigational product and through the final study visit will be recorded on the appropriate eCRF (using their generic and brand name, if known) with the corresponding indication, start and stop dates. At each study visit, subjects will be asked whether they have started or discontinued any medication since their previous study visit. This includes single use or PRN (as needed) medication use.

Previous treatment of rosacea must be recorded irrespectively of the term it was given. Corresponding condition shall be captured in the subject's Medical History.

11.1.4 Vital Signs

Vital signs will be collected at each visit. Blood pressure readings will be obtained at every visit as described in the Schedule of Study Activities. Subject should be asked to remove all clothing that covers the location of cuff placement. The individual should be comfortably seated in the chair, with the legs uncrossed, and the back and arm supported, such that the middle of the cuff on the upper arm is at the level of the right atrium (the mid-point of the sternum). Neither the subject nor the observer should talk during the measurement. After 5 minutes sitting, serial clinic BP measurements and heart (x3) rate will be performed, using the non-dominant arm with a calibrated electronic sphygmomanometer. The average of the second and third readings will be documented.

Any abnormal characteristics will be evaluated by the Investigator based on their significance. Abnormal vital signs will be considered AEs if they require therapeutic medical intervention, and/or if the Investigator considers them to be AEs based on his/her clinical judgement.

11.1.5 Physical examination

Physical examination, including height, weight, and evaluation of organs and systems (General Appearance, Heart/Cardiovascular, Lungs, Gastrointestinal, Ears / Nose / Throat, Extremities, and Skin) will be assessed at the Screening, Baseline and EOS/ET visits.

Clinically significant abnormalities other than presence of rosacea lesions will disqualify subject from participation.

11.1.7 Clinician’s Erythema Assessment (CEA)

Clinician’s Erythema Assessment (CEA) will be will be evaluated at each study visit. The Investigator will assess the extent of rosacea based on the 5-point severity scale summarized below.

The Investigator will perform a static (“snap-shot”) evaluation of erythema severity using the CEA, and report the one integer that best describes the overall severity beginning from the Baseline Visit (Table 4). Although inflammation (papules, pustules, plaques) or dry appearance may obscure the level of erythema, underlying redness should be evaluated disregarding this effect. Inflammation or dry appearance may be noted, but perilesional erythema should not be included in this assessment. Transient erythema (flushing) will also not be included.

Table 4. Clinician Erythema Assessment

Score	Severity	Description
0	Clear	Clear skin with no signs of erythema
1	Almost clear	Almost clear, slight redness
2	Mild	Mild erythema; definite redness
3	Moderate	Moderate erythema; marked redness
4	Severe	Severe erythema; fiery redness

Questionnaire can be found in [Appendix 2](#).

11.1.8 Skindex 16

Skindex-16 instrument will be evaluated at each study visit. The participant will answer a questionnaire examining the relationship between the patient’s skin health and quality of life. Skindex16 questionnaire can be found in [Appendix 4](#).

11.1.9 Patient Self-Assessment (PSA)

Subjects will be asked to perform static (“snap-shot”) evaluations of their rosacea-associated facial erythema severity using the Patient Self Assessment scale (PSA) at each study visit, and report the one integer that best describes the overall severity of their facial redness as seen in a mirror at the time of the evaluation.

Table 5: Patient Self-Assessment

Circle the number that best describes your rosacea-related facial redness RIGHT NOW.		
Score	Severity	Description
0	No redness	Clear of unwanted redness
1	Very mild redness	Nearly clear of unwanted redness
2	Mild redness	Somewhat more redness than I prefer
3	Moderate redness	More redness than I prefer
4	Severe redness	Completely unacceptable redness

Questionnaire can be found in [Appendix 3](#).

11.1.10 Telangiectasia Evaluation

Telangiectasia evaluation will be performed at Baseline and Week 8 visit as indicated in the Schedule of Study Activities. The Investigator will assess the extent of telangiectasia based on the 4-point severity scale summarized below.

The Investigator will perform a static (“snap-shot”) evaluation of telangiectasia severity using the below scoring system.

Table 6: Telangiectasia Evaluation

Score	Grade	Definition
0	Clear	No telangiectasia
1	Mild	Only few fine vessels discernible, involves 10% or less of the facial area
2	Moderate	Multiple fine vessels and/or few large vessels discernible, involves > 10% - 30% of the facial area
3	Severe	Many fine vessels and/or large vessels discernible, involves > 30% of the facial area

Questionnaire can be found in [Appendix 6](#).

11.2 Safety Assessments

11.2.1 Assessment of Adverse Events

Beginning with the screening visit and through the EOS/ET visit, the Investigator and study personnel will review each subject's clinical evaluation findings and query the subject directly regarding AEs (see [Section 12](#), Safety Data Collection, Recording and Reporting). Subjects must be followed for AEs until 30 days post study conclusion or until the PI determines AEs are stable, whichever is later.

11.2.2 Pregnancy Test

A urine pregnancy test will be performed at all visits for females of childbearing potential. The baseline result must be available and must be negative before the subject apply the first application of investigational product. Positive pregnancy test will disqualify the subject from the participation.

11.2.3 Laboratory Assessments

Blood samples will be taken at the times indicated in the [Schedule of Study Activities](#). Blood samples should be taken using standard venipuncture techniques. Blood sampling will be performed according to the site SOPs.

The following routine clinical chemistry, hematology and Lipid Panel will be performed according to the Schedule of Study Activities. Albumin, Alkaline Phos, ALT, AST, Total Bilirubin, BUN, BUN:Creatinine ratio, Calcium, Chloride, Creatinine, eGFR, Glucose, Potassium, Sodium, Uric Acid.

Lipid Panel: HDL Cholesterol, LDL cholesterol, Total Cholesterol, Triglycerides, VLDL Cholesterol, LDL/HDL Cholesterol Ratio, Non HDL Cholesterol.

Hematology: WBC, RBC, Hemoglobin, Hematocrit, Platelets, WBC Differential (Neutrophils, Lymphocytes, Monocytes, Eosinophils, Basophils), HbA1C.

Serology will only be done at Screening: HIV Ab, HCV Ab, HBsAg.

Urinalysis will be performed according to the Schedule of Study Activities.

Patients will be asked to fast for at least 8 hours before all blood tests are done.

The total blood volume collected for clinical labs for Screening visit will be approximately 20 ml of whole blood. Volume collected for subsequent visits would be approximately 10 ml of whole blood.

Any value outside the normal range will be flagged for the attention of the Investigator or designee at the site. The Investigator or designee will indicate whether or not the value is of clinical significance. If the result of the clinical chemistry test from the samples taken during the screening phase is indicated as clinically significant, the study subject will NOT be allowed into the study.

11.2.4 Biomarkers

In addition to the blood drawn for the safety laboratory assessments, additional blood will be collected for the biomarker analysis at the times indicated in the Schedule of Activities. Samples will be processed on site and aliquots stored in the -80° C freezer. Approximately 20 ml of whole blood will be drawn for biomarkers at each visit. Subjects will be asked to fast for at least 8 hrs. before blood for biomarkers is drawn. Biomarkers will be evaluated for cytokines, chemokines, inflammatory markers and immune response.

11.2.5 Samples Shipment

All clinical chemistry samples are to be shipped to the central laboratory where samples will be analyzed. Biomarker samples are to be shipped frozen monthly on dry ice to the central laboratory. Shipments should be made only on Mondays and Tuesdays to ensure receipt of the specimens by Friday.

11.2.6 Treatment Adherence Evaluations

11.2.6.1 Study Diary Compliance Review

The subject will be given a Study Diary at each study visit of the treatment period to record date and time of applications, any adverse events, quality of life assessments, of the investigational product. Subjects will record every application during the treatment period and will bring the Subject Diary to each of the post-baseline study visits for compliance review. The Investigator will verify that the subject complied with the application requirements and will file the completed Subject Diary in the study files at each study visit until the EOT/ET visit. Any missed application notations will be clarified with the subject and documented in the subject's CRF.

11.2.6.2 Treatment Compliance

Each site participating in the trial will be instructed to assess subject's compliance by weighing the investigational product and obtaining the weight of the bottles in grams pre- and post-application. Study personnel will be asked to take out the bottles from the carton, weigh both bottles and record the weight pre-first application. At the Day 28 and Day 56 visit, study personnel will need to weigh both bottles without the carton and record the weight. This procedure should be followed every time study medication is dispensed and returned. Sites will be provided scales, which will be calibrated prior to each use. Study personnel will be instructed to record measurements into the eCRF.

12 SAFETY DATA COLLECTION, RECORDING AND REPORTING

The Investigator will monitor each subject for clinical evidence of adverse events on a routine basis throughout the study. The Investigator will assess and record any Adverse Event (AE) in detail including the date of onset, description, severity, time course, duration and outcome, relationship of the adverse event to investigational product, an alternate etiology for events not considered “related” or “probably related” to investigational product, final diagnosis, if known, and any action(s) taken. For AEs to be considered intermittent, the events must be of similar nature and severity and each intermittent AE will be reported separately. AEs and SAEs, whether in response to a query, observed by site personnel, or reported spontaneously by the subject will be recorded, monitored and followed-up until the resolution (or until the Investigator deems the event to be stable/chronic).

12.1 Definitions

12.1.1 Adverse Event

An AE is defined as any untoward medical occurrence in a Subject or clinical investigation subject administered a pharmaceutical product and which does not necessarily have a causal relationship with this treatment. An AE can therefore be any unfavorable and unintended sign (including an abnormal laboratory finding), symptom, or disease temporally associated with the use of a medicinal (investigational) product, whether or not the event is considered causally related to the use of the investigational product.

Such an event can result from use of the drug as stipulated in the protocol or labeling, as well as from accidental or intentional overdose, drug abuse, or drug withdrawal. Any worsening of a pre-existing condition or illness is considered an AE. If a new rosacea sign or symptom or worsening of a rosacea sign or symptom was believed by the investigator to be related to the investigational product and not the disease, then it will be recorded as an AE. Clinically significant abnormalities are to be followed to resolution (i.e., become stable, return to normal, return to baseline, or become explainable). Laboratory abnormalities and changes in vital signs are considered to be AEs only if they necessitate therapeutic medical intervention, and/or if the Investigator considers them to be AEs.

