6.5 Treatment Assignment (Randomization)

Randomization will be performed using an Interactive Web Response System (IWRS) at the time the subject has met all eligibility criteria and is ready for enrollment. Subjects will be randomized in a 1:1 ratio to receive either B244 or vehicle and will be stratified by site.

Interactive Web Response System (IWRS) will assign subjects to the treatment arm and specify the kit number to be dispensed.

The randomization scheme will be generated and held by the independent third party throughout the conduct of the study and will not be available to the Sponsor, Investigator, or study staff, or to clinical staff who could have an impact on the outcome of the study.

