6.6 Blinding/Unblinding Procedures

This is a double-blind study, thus Sponsor, CRO, site staff, study monitors, and subjects will be blinded to the randomization scheme. The packaging of the investigational product products will be identical in appearance to make difference in treatment less obvious to the subjects.

The blinding scheme for each set of the investigational product will be available to the FDA or other regulatory agency investigators at the time of site inspection to allow for verification of the treatment identity of each subject.

The blinding code must not be broken except in emergency situations for which the identification of the study treatment of a subject is required by the Investigator to complete a serious adverse event report. In such situations, the Investigator will use the IWRS system in order to unblind the treatment for the individual subject. Unblinded information will be held by designated individual(s), and the date and reason for breaking the blind must be recorded and reported appropriately to the IRB.

As the study is blinded, the Investigator should promptly document and explain to the Sponsor and Medical Monitor any premature unblinding (e.g., accidental unblinding, unblinding due to a serious adverse event) of the investigational product(s).

The Investigator may unblind a participant's treatment assignment only in the case of emergency or in the event of a serious medical condition when knowledge of the study treatment is essential for the appropriate clinical management or welfare of the participant, as determined by the Investigator. It is preferred (but not required) that the Investigator first contacts the Medical Monitor to discuss options before unblinding the participant's treatment assignment. The Investigator must notify the Sponsor as soon as possible when a participant's treatment assignment is unblinded without revealing the treatment assignment of the unblinded participant unless that information is deemed important for the safety of participants currently in the study. The date and reason for the unblinding must be documented in the participant's study record.

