12.3 Causality of Adverse Events

The Investigator will use the following definitions to assess the relationship of the AE/SAE to the use of investigational product:

Related	The event occurred within a reasonable time after drug administration or drug concentration and body fluids demonstrated that the investigational product was present: the event could not be reasonably explained by known characteristics including concomitant therapies; the adverse event abated after discontinuing the investigational product.
Probably Related	The event has a strong temporal relationship to investigational product or recurs on re-challenge and another etiology is unlikely or significantly less likely.
Possibly Related	The event has a strong temporal relationship to the investigational product and an alternative etiology is equally or less likely compared to the potential relationship to investigational product.
Probably Not Related	The event has little or no temporal relationship to the investigational product and/or a more likely alternative etiology exists.
Not Related	The event is due to an underlying or concurrent illness or effect of another drug and is not related to the investigational product (e.g., has no temporal relationship to investigational product or has a much more likely alternative etiology).

If an Investigator's opinion of possibly, probably not, or not related to investigational product is given, an alternate etiology must be provided by the Investigator for the AE.

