14 DATA ANALYSIS

The data analysis will be conducted on all participant data when the trial ends. Data will be presented by treatment group and overall.

Categorical variables will be summarized by frequency distributions (number and percentages of subjects) and continuous variables will be summarized by descriptive statistics (mean, standard deviation, etc.).

Adverse events will be summarized by treatment group using the Medical Dictionary for Regulatory Activities (MedDRA) system organ class and preferred term. Separate tabulations will be produced for all treatment-emergent AEs (TEAEs), treatment-related AEs (those considered by the Investigator as at least possibly drug related), SAEs, discontinuations due to AEs, and AEs \geq Grade 3 severity. By-subject listings will be provided for any deaths, SAEs, and AEs leading to discontinuation.

Descriptive statistics for each treatment group will be provided for clinical laboratory values (e.g., hematology, serum chemistry, and urinalysis) and vital signs data, presented as both actual values and changes from baseline relative to each on-study evaluation. Abnormal clinical laboratory values will be listed.

All data will be provided in by-subject listings.

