3.2 Study Endpoints

3.2.1 Safety & Tolerability (Primary)

Safety and tolerability endpoints will consist of all adverse events reported during the study duration.

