6.5.2 Safety Population

The safety population includes all randomized subjects who received investigational product.

6.5.3 mITT Population

A modified intent-to-treat population includes all subjects who are randomized, applied at least one dose of assigned product, and returned for at least one post-baseline evaluation visit.

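### Protocol 12.1.1 leaves open whether rosacea worsening put down to the disease is an adverse event, and no planned by-arm output counts subjects who worsened

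*Protocol*

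**What the plan says.** **AE definition.** Protocol 12.1.1 does not require a causal link for an event to be an AE, and adds: "Any worsening of a pre-existing condition or illness is considered an AE". Every subject enters with rosacea, so on its own this covers every flare. The next sentence says that a new or worse rosacea sign that "was believed by the investigator to be related to the investigational product and not the disease, then it will be recorded as an AE". The contrary case is not mentioned.

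**Causality and tabulation.** Under Protocol 12.3 an event is possibly related when it has a strong temporal relationship to the product and "an alternative etiology is equally or less likely compared to the potential relationship to investigational product". Protocol 14 tabulates "treatment-related AEs (those considered by the Investigator as at least possibly drug related").

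**Endpoint.** SAP version 2, section 3.2.1: "Safety and tolerability endpoints will consist of all adverse events reported during the study duration". SAP 8.2.1 makes the reporting descriptive.

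**Planned by-arm displays (SAP version 2).**
- The shell for change in IGA, CEA and PSA (Tables 14.2.1.1 to 14.2.3.2) has rows for 1, 2 and 3 grades, with no sign and no row for no change or worse.
- Tables 14.2.6 to 14.2.9 count 2-grade improvement and scores of 0 or 1.
- The supplemental analysis in 8.3 concerns improvement, within-group tests of change to Week 8, and a subgroup with a baseline score of 3.
- The sensitivity tables (14.2.10.1 to 14.2.10.3) and the Skindex-16 tables give summary statistics of change.
- The frequency figures have titles but no layout.

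**SAE definition.** SAP 6.7.6 omits the category of other important medical events, which Protocol 12.1.2 includes.

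**The concern.** A relapsing skin disease will produce flares on a facial spray, and whether B244 produces more of them than vehicle is a central tolerability question. If one site records every flare and another records only those blamed on the product, the AE rate reflects reading habits as well as the product.

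A flare of uncertain cause is the awkward case. Under 12.3 it could be rated possibly related, and Protocol 14 would then count it as treatment-related. Under the narrow reading of 12.1.1 it may never be entered as an AE, so 12.3 is never applied to it.

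The clinical scores should be the fallback, but no planned output turns them into a count of subjects who got worse in each arm.

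**Working it through.** The documents state no rate for flares or AEs in this trial and plan no test on AEs, so there is no figure to reproduce. The check has two parts.

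**1. The two sentences side by side**
- *Read as an addition.* The rosacea sentence says if, not only if, although the same paragraph uses the stricter form for laboratory abnormalities. But then it adds nothing, because the preceding sentence already covers all worsening.
- *Read as an exception.* It then has a purpose, to keep ordinary disease fluctuation out of the AE data. But it lacks the words that would make it an exception.

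Each reading has textual support, and no other section chooses between them.

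**2. What the reading could do to the AE table (illustration only)**

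From the documents: 130/2 = 65 per arm enrolled and 104/2 = 52 per arm completing. Assumed: true flare rates pV = 20% (vehicle) and pB = 30% (B244), and the recording shares below.

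Formulas:
- Equal share r of all flares recorded in both arms: recorded rates are r·pB and r·pV, and the difference is r·(pB − pV). The ratio pB/pV does not change.
- Recording that follows cause, with share s of drug-caused and share f of background flares recorded: B244 rate = s·(pB − pV) + f·pV; vehicle rate = f·pV.
- Chance of no excess on B244 = P(X_B ≤ X_V), with independent binomial counts.

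| Recording pattern | B244 | Vehicle | Difference (points) | No excess, 65 per arm |
|---|---|---|---|---|
| All recorded | 30% (19.5 subjects) | 20% (13.0) | 10 | 11% |
| Equal share, r = 0.5 | 15% (9.8) | 10% (6.5) | 5 | 23% |
| Equal share, r = 0.25 | 7.5% (4.9) | 5% (3.3) | 2.5 | 34% |
| s = 0.8, f = 0.1 | 10% (6.5) | 2% (1.3) | 8 | 3% |
| s = 0.8, f = 0.25 | 13% (8.5) | 5% (3.3) | 8 | 7% |
| s = 0.5, f = 0.1 | 7% (4.6) | 2% (1.3) | 5 | 11% |

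With 52 per arm, the first three rows give 14%, 27% and 37%. Other assumed rates at 65 per arm, for r = 1, 0.5 and 0.25: 10% vs 20% gives 7%, 18% and 30%; 20% vs 40% gives 1%, 7% and 18%.

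*Attribution that differs by arm, with no true effect.* If half of flares are recorded on B244 and a quarter on vehicle, a true rate of 10% in both arms gives 5% vs 2.5%, and a true rate of 20% gives 10% vs 5%. That is a spurious difference of 2.5 to 5 points.

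So the AE level moves under every incomplete pattern, while the contrast can weaken, stay as visible, become clearer or be biased.

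**The case against.** **Dilution is not a given.** A reader might infer that the narrow reading must dilute a true difference. The documents do not support that. The narrow reading selects on believed cause, and an investigator who judges cause well removes background noise: with s = 0.8 and f = 0.1 the chance of seeing no excess falls from 11% to 3%. This objection stands, so dilution is one possibility among several.

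**Randomization and blinding.** A reader might also infer that neither arm can be favoured, because "Subjects will be randomized in a 1:1 ratio to receive either B244 or vehicle and will be stratified by site" and "This is a double-blind study, thus Sponsor, CRO, site staff, study monitors, and subjects will be blinded to the randomization scheme". That does not follow either. Protocol 6.2 describes B244 as cloudy and light pink and the vehicle as clear and colorless. The identical white bottles (6.3) may hide this in part, but equal attribution by arm cannot be assumed.

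**Other planned outputs.** It would be too strong to say that nothing planned could reveal an excess of flares. The sensitivity tables give mean, SD and quartiles of IGA, CEA and PSA change by arm, and the Skindex-16 tables give the mean, median and range of change. A net excess could show there, and subject listings exist. None of these is a count of subjects who worsened.

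**Capture between visits.** After baseline, scores are scheduled on Days 7, 28, 56 and 84. An investigator may see a worsening subject at an unscheduled visit (Protocol 10.2.8), the diary collects adverse events (11.2.6.1), and Skindex-16 covers the past week. These lessen the gap, but none says which flares count as AEs.

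**Causality.** Possibly related requires a strong temporal relationship, so 12.3 could give an uncertain flare that rating but need not.

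**Conclusion.** The point holds, in measured form. The paragraph is ambiguous on an event expected in this disease, the ambiguity feeds the primary endpoint, and no planned by-arm output counts subjects whose rosacea worsened. The AE level depends on the reading. The direction of any effect on the between-arm difference is not determined, and its size cannot be estimated, because flare rates and recording shares are not documented; every percentage in the illustration rests on assumed values. Because the safety analysis is descriptive, no error rate is affected; the harm is to how the AE table can be interpreted. The point is worth correcting because the remedy is cheap, but it does not invalidate the design.

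The missing SAE category in SAP 6.7.6 is a separate mismatch between the documents and does not bear on rosacea worsening.

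**What to change.** 1. **Protocol 12.1.1.** Reconcile the two sentences so that the status of worsening attributed to the disease, or of uncertain cause, is explicit. The sponsor may make all worsening an AE with causality rated separately under 12.3, or make it a stated exception with its own capture route and threshold. If data collection is complete, state in the SAP which reading sites used.
2. **Tables 14.2.1 to 14.2.3.** Split the grade rows into improved, no change and worse. With the safety results in SAP 8.2.1, report by arm the number of subjects with at least 1-grade worsening from baseline in IGA, CEA and PSA, at each visit and at any post-baseline visit, including Early Termination and any unscheduled scores. Use the Safety population and show how many subjects have a post-baseline score. The mITT set might seem enough, since it takes randomized subjects who "applied at least one dose of assigned product, and returned for at least one post-baseline evaluation visit", but SAP 6.5.4 and 8.2 assign safety analyses to the Safety population.
3. **SAP 6.7.6, as a separate item.** Add other important medical events, to match Protocol 12.1.2.

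Optional: a discontinuation row for worsening or lack of effect in Tables 14.1.1.1 and 14.1.1.2, if the eCRF records that reason.

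**Cost.** Item 1 needs a short amendment with IRB approval (Protocol 19) or an SAP note. Item 2 uses scores already collected. SAP 6.4 lets layout change without a revision, so only the worsening count and the SAE definition need new SAP text. If the broad reading is chosen, AE counts may rise in both arms.
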